COmpletion Sentinel Node resection with or without minimally invasive and endoscopic cooperative surgery following non-curative Endoscopic Submucosal Dissection for Early Gastric Cancer (Co-SNARE-EGC trial)

Background

Early gastric cancer (EGC) is defined as a tumor confined to the mucosa or submucosal layers without lymph node involvement (1). Patients with EGC are typically recommended endoscopic submucosal dissection (ESD) as the first-line treatment, provided they meet the inclusion criteria. The current expanded indications for ESD in EGC include differentiated cancer without ulceration, regardless of size; differentiated cancer with ulceration, provided the lesion is no larger than 3 cm; and undifferentiated cancer without ulceration, with a maximum size of 2 cm(2,3). In some cases, patients may be classified as non-curative (eCuraC2) after ESD due to positive vertical margins, deep submucosal invasion, or lymphovascular invasion. In such instances, complementary surgery is generally recommended (2,3). Gastrectomy with lymphadenectomy carries a risk of severe complications (Clavien-Dindo grade >IIIa) ranging from 8.9% to 22% (4-6), and can significantly affect the patient's health-related quality of life (7). Moreover, many patients may have no residual disease after surgery. A recent multi-center Western study found that 33% of patients who underwent gastrectomy following non-curative ESD had residual tumor, either locally or in regional lymph nodes (8).

Local injection of indocyanine green (ICG) into the peritumoral area has been reported in gastric cancer surgery to identify sentinel lymph nodes, visualize draining lymph nodes, and assess the completeness of lymph node dissection (9). In this phase 1 trial, we aim to evaluate ICG-guided regional lymph node resection, including sentinel node (SN) identification, with complementary laparoscopic and endoscopic cooperative surgery (LECS) as an alternative to gastrectomy following non-curative ESD. For patients with radical but non-curative ESD, ICG-guided SN resection will be performed, while in those with non-radical ESD, LECS combined with ICG-guided SN resection will be performed.

Study design

A single-center, phase-1, prospective non-randomized trial.

Scientific objectives

To study the safety and feasibility of ICG-guided SN with or without additional LECS as an alternative treatment for EGC with previous non-curative ESD

Primary outcome measures

- Safety, defined as Clavien-Dindo complication grade >/= III

Secondary outcome measures

- Any complication (Clavien-Dindo II-IV)
- Postoperative bleeding requiring blood transfusion
- Leakage/postoperative abscess requiring drainage
- Operation time
- pT
- Radicality
- Number of lymph nodes
- Number of positive lymph node
- Hospital-stay
- Health-related quality of life
- 30-day mortality,
- In-hospital mortality
- 1-year disease-free survival

Study population

Patients with EGC previously treated with ESD at our institution will be eligible for inclusion in the study if the resection is non-curative

Inclusion criteria

- EGC previously treated with ESD according to current guidelines (differentiated adenocarcinoma Ulcerative- any size, differentiated adenocarcinoma Ulcerative+ </=3cm, undifferentiated adenocarcinoma Ulcerative- </=2cm)
- Non curative resection
 - LVI positive
 - R1 vertical margin
 - deep submucosal invasion >Sm1
- Signed informed consent

[figure not shown]
Exclusion criteria

- Location within 2 cm from cardia or pylorus
- Non-curative resection with only R1 horizontal margin
- Inoperative because of severe comorbidities
- Previous radiotherapy to the upper abdomen
- Pregnancy
- Allergy to ICG
- Inability to provide informed consent due to cognitive impairment, language barrier, or other reasons impairing understanding and autonomous decision-making.

The procedure

ICG-guided sentinel node (SN) resection will be performed by endoscopically injecting 0.5 ml of 100-fold diluted ICG at four sites around the tumor scar, followed by resection of the positive lymph nodes after a 15-20 minutes waiting period. LECS will be performed through a combination of endoscopic marking around the scar, dissection using a knife, perforation of the gastric wall, and subsequent laparoscopic resection of the area under endoscopic guidance.

Study flowchart

	Preop visit	ICG guide d SN +/- LECS	Postop visit (30 days)	3 months postop - CT + gastroscopy	6 months postop - CT + gastroscopy	9 months postop - CT + gastroscopy	12 months postop - CT + gastroscopy
Information and consent form	x						
Physical & laboratory evaluation	x		x	x	x	x	x
HQL-questionnaires	x		x				x
Review of medical charts			x				x

Assessment of safety

Complications will be continuously monitored for each procedure according to the clinic's routines. An interim analysis will be performed for each 3 cases completed. If any death is observed directly attributed to the procedure the study will be prematurely discontinued. Moreover, the study will also be discontinued if severe complications (Clavien-Dindo complication grade \geq III) are observed in $> 20\%$ of cases, which is the expected rate for gastrectomy (6).

Follow-up

All patients will undergo an initial postoperative follow-up at the outpatient clinic 30 days after the procedure. Subsequent follow-up visits will occur every 3 months during the first year. During this period, surveillance will include both endoscopic (gastroscopy) and radiological (computed tomography) assessments at 3-month intervals. After the first year, patients will be followed according to the clinic's standard protocol, consisting of physical examination, radiological imaging, and endoscopic evaluation every 6 months for a total follow-up period of 5 years. For patients who die before completing follow-up, the date of death will be documented.

Sample size

We aim to include 10 patients in the study.

Sample size justification

Because this is a pilot study no power calculation is deemed necessary.

Management of data

Information and data from patients included in the study will be handled only by researchers working under confidentiality according to the Health and Healthcare Act. The data will be collected in a database and pseudonymized with study-specific patient codes. All study documentation will be stored in a locked, protected location intended for handling confidential information at Karolinska University Hospital in Stockholm. Only personnel delegated for the study as well as the monitor will have, under confidentiality protection, access to patient records and source data. The code key in these cases will be handled by the appointed research coordinator at the Medical Unit of Upper Abdomen, Karolinska University Hospital in Stockholm. The data material will be destroyed 10 years after publication.

Ethics

The study is conducted in compliance with the protocol and in accordance with the ethical principles of the second Declaration of Helsinki and with GCP rules. The EU General Data Protection Regulation (GDPR) will be respected. The rights, safety and well-being of the trial subjects are the most important considerations and should prevail over the interests of science and society. Study personnel conducting this trial are qualified by education, training, and experience to perform their respective tasks.

Dissemination of knowledge and publication strategy

The study will be registered at www.clinicaltrials.gov. The protocol will be internationally exposed through a separate publication. Positive as well as negative or inconclusive results will be submitted for publication in international peer-reviewed journals and oral presentations at relevant national and international congresses.

Competing interests

We declare no support and no financial relationships with any organizations that might have an interest in the submitted work.

References

1. Murakami T. Early cancer of the stomach. *World J Surg*. 1979 Nov;3(6):685–92.
3. Japanese Gastric Cancer Treatment Guidelines 2021 (6th edition). *Gastric Cancer Off J Int Gastric Cancer Assoc Jpn Gastric Cancer Assoc*. 2023 Jan;26(1):1–25.

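### Do the secondary outcomes pT and Radicality need a named specimen, given that patients without LECS have no gastric specimen from the study operation?

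*Protocol*

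**What the plan says.** The Protocol's Background assigns the operation by the result of the earlier ESD: "For patients with radical but non-curative ESD, ICG-guided SN resection will be performed, while in those with non-radical ESD, LECS combined" with node resection. The Scientific objectives accordingly cover "ICG-guided SN with or without additional LECS as an alternative treatment for EGC with previous non-curative ESD", so patients without LECS are expected.

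The section The procedure describes what each operation removes. Node resection is the ICG injection around the scar, "followed by resection of the positive lymph nodes after a 15-20 minutes waiting period". LECS adds dissection around the scar, "perforation of the gastric wall, and subsequent laparoscopic resection of the area under endoscopic guidance". Only LECS yields gastric wall.

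Under Secondary outcome measures, pT and Radicality are single-term entries. No specimen, margin definition or patient subset is attached. They follow operation time and precede the two lymph node counts. The Inclusion criteria use "R1 vertical margin" as one of the features that make the earlier ESD non-curative.

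The Sample size section plans 10 patients and gives no split between the two operations.

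**The concern.** Outside the outcome list, radical describes only the ESD done before the trial. Carried over to the outcome, Radicality would be the feature that assigned the operation: known before surgery, positive in every patient without LECS and negative in every patient with it. pT would have a similar problem, because the Background says that early gastric cancer "is defined as a tumor confined to the mucosa or submucosal layers", so the ESD depth would be one of two layers in everyone.

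If the study operation is meant instead, patients with node resection alone have no gastric specimen and neither outcome is defined for them. A third option, final status over all 10 patients, would count margins obtained before the trial as successes.

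The flowchart does not name the specimen either. It has no pathology row, and "Review of medical charts" at 30 days and 12 months could pick up either report.

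At stake would be the one listed pathology outcome that shows whether LECS completed the resection. Its reported value could depend on a denominator chosen after the results are known.

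**Working it through.** The Protocol gives no figure for either outcome, so there is nothing to reproduce. The check is first a reading of the text, then a sizing of what stays open.

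**Which specimen is meant**

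- Position: the neighbouring entries (operation time, number of nodes, number of positive nodes) are all results of the study operation.
- Timing: the ESD precedes enrolment and is an entry condition. Its margin and depth are baseline facts and cannot be outcomes of this trial.
- Wording: in the Background, radical and non-radical are each attached to ESD. That describes the ESD; it does not define the outcome.
- pT: the Background's definition of early gastric cancer also excludes nodal involvement, yet positive nodes are counted as an outcome. The definition therefore does not limit what surgery may show. Where the ESD had a positive vertical margin, depth beyond the ESD specimen is unknown, so the pT of the LECS specimen is informative.
- Flowchart: it has no row for operation time, complications, node counts or hospital stay either. The missing pathology row says nothing particular about these two outcomes.

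The ESD reading drops out.

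**What stays open: the denominator for Radicality**

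Inputs: N = 10 (Sample size). The number of LECS patients, m, is not given; 3 to 7 is assumed. The number of margin-free LECS specimens, k, is assumed.

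- LECS specimens only: k/m.
- Final status over all patients: (10 − m + k)/10.
- Difference: (10 − m + k)/10 − k/m = (10 − m)(m − k)/(10m).

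| m | k | LECS only | All 10 | Difference |
|---|---|---|---|---|
| 3 | 2 | 2/3 = 67% | 9/10 = 90% | 7 × 1/30 = 23 points |
| 5 | 4 | 4/5 = 80% | 9/10 = 90% | 5 × 1/50 = 10 points |
| 7 | 5 | 5/7 = 71% | 8/10 = 80% | 3 × 2/70 = 9 points |

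When k = m the difference is zero and both give 100%. The exact (Clopper-Pearson) 95% intervals are 28.4 to 99.5% for 4/5 and 55.5 to 99.7% for 9/10. They overlap almost entirely, and neither supports more than a description.

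**What stays open: pT when no tumour is left**

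The Background cites a study in which "33% of patients who underwent gastrectomy following non-curative ESD had residual tumor, either locally or in regional lymph nodes". That figure combines local and nodal disease after gastrectomy, so it is not a local rate in patients with a non-radical ESD. A local residual rate r of 20 to 60% is assumed, with m = 5:

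- Expected patients with tumour to stage: m × r = 5 × 0.20 = 1.0 to 5 × 0.60 = 3.0.
- Chance that none has any: (1 − r)^5 = 0.80^5 = 33% to 0.40^5 = 1%.

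A category for no residual tumour will probably be needed. A pathology report on a specimen without tumour says so, and the analyst records it.

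**The case for a change.** The best case for a change is that what an outcome measures, on which specimen and in whom, is its definition and belongs in the protocol, not in an analysis plan. Other entries in the same list are qualified: bleeding by transfusion, leakage by drainage, survival by its time point. Even if the LECS specimen is accepted as meant, the text does not choose between LECS patients and all 10, and over all 10 the result cannot fall below (10 − m)/10, which is 70%, 50% or 30% for m = 3, 5 or 7, even if every LECS margin is positive. Naming the specimen would cost a few words.

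Much of this stands as fact: the entries are bare, the denominator is unwritten, and the floor is correct arithmetic. It does not make the plan wrong. No two sections contradict each other on these outcomes and nothing false is stated about them. An outcome that can be assessed only where gastric wall was removed has an evaluable subset that follows from the description of the operations. The percentages rest on assumed values of m and k. The freedom to choose a denominator late carries little weight, because no decision depends on the choice and a listing by operation shows both numerator and denominator.

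**Conclusion.** No change is needed; this is a gap that analysts fill sensibly. They would report pT and Radicality for the LECS specimens, by operation, and keep ESD depth and margins as baseline data. Naming the specimen in the outcome list would only write down that practice.

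The size is small. With m assumed between 3 and 7, the examples above differ by 9 to 23 percentage points between the two denominators, on one or two patients with positive margins, and by nothing if all LECS margins are free. The primary safety outcome does not use either entry. The discontinuation rules under Assessment of safety rest on procedure-related death and on complications of Clavien-Dindo grade III or higher in more than 20% of cases. No hypothesis is tested on pT or Radicality.

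The conclusion assumes that results will be shown by operation, which is easy with 10 patients and two named operations, and that the entries mean the study specimen, as their place in the list indicates.

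### Does pooling sentinel node resection alone with sentinel node resection plus LECS in the safety count hide an excess risk from LECS?

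*Protocol*

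**What the plan says.** The Background section of the protocol sets out the two operations. The first leaves the stomach wall alone: "For patients with radical but non-curative ESD, ICG-guided SN resection will be performed". The second operation is the larger one, and the protocol assigns it by contrast: "while in those with non-radical ESD, LECS combined with ICG-guided SN resection will be performed". Under The procedure, only LECS is described as involving "perforation of the gastric wall, and subsequent laparoscopic resection of the area under endoscopic guidance".

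The Scientific objectives section covers both operations in a single aim: "To study the safety and feasibility of ICG-guided SN with or without additional LECS as an alternative treatment". The primary outcome is "Safety, defined as Clavien-Dindo complication grade >/= III". The secondary outcomes include leakage or abscess needing drainage, bleeding needing transfusion, any complication of grade II to IV, and 30-day and in-hospital mortality.

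Assessment of safety begins with continuous monitoring of complications for each procedure. It then states: "An interim analysis will be performed for each 3 cases completed". A death directly attributed to the procedure ends the trial, and "the study will also be discontinued if severe complications" exceed 20% of cases, the rate the protocol expects for gastrectomy. Under Sample size: "We aim to include 10 patients in the study". No number per operation is set.

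**The concern.** The two operations differ in what is done to the stomach, so their risks of a severe complication may differ. The stopping count has one denominator, and the mix of operations is whatever arrives. If SN resection alone is safer, its patients dilute the rate. One event among cases 4 to 6 gives 1/6 = 16.7%, and the trial continues. If that event was in a LECS patient, and 2, 3 or 4 of the six had LECS, the LECS rate is 50%, 33% or 25%.

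With looks after 3, 6 and 9 cases, a trial that reaches case 10 must also end at or below 20% pooled. A reader could take that figure as evidence that both operations are as safe as gastrectomy or safer, and carry an unproven claim about LECS into a later study.

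**Working it through.** **Inputs.** From the protocol: 10 patients, a look after every 3 cases, and a stop when the observed rate exceeds 20%. Not in the protocol, and so assumed: the severe-complication risk of each operation (p_L for LECS, p_S for SN alone) and the number f of LECS patients among the ten. The protocol gives no power calculation, so there is no figure of its own to reproduce beyond the limit.

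**What the rule allows.** If the limit is applied at the looks:

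| Cases | Events that stop | Most events allowed |
|---|---|---|
| 3 | 1 (33.3%) | 0 |
| 6 | 2 (33.3%) | 1 (16.7%) |
| 9 | 2 (22.2%) | 1 (11.1%) |

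A trial that reaches case 10 has had at most one event, in cases 4 to 9, and ends at no more than 2/10 = 20%.

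**Does that ceiling come from pooling?** No. The table contains no reference to the type of operation. If all ten patients had LECS, the same limits would apply and the trial would again end at 2/10 or less. The ceiling follows from frequent looks at a small number of cases.

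**How often would masking occur?** Masking here means reaching case 10 with an observed LECS rate above 20%. All orderings of the f LECS patients are taken as equally likely.

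For f of 5 or more, one LECS event is at most 1/5 = 20%, which is not above the limit. Two LECS events are needed, one in cases 4 to 9 and the other in case 10:

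P = (f/10) · p_L · [6(f−1)/9] · p_L · (1−p_L)^(f−2) · (1−p_S)^(10−f)

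With f = 5, p_L = 0.40 and p_S = 0.05: 0.5 × 0.4 × 2.667 × 0.4 × 0.6³ × 0.95⁵ = 0.036.

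For f of 2 to 4, one LECS event is enough. Exact enumeration gives:

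| Assumed risk, LECS / SN alone | f = 2 | f = 3 | f = 4 | f = 5 | f = 6 to 9 |
|---|---|---|---|---|---|
| 40% / 5% | 25.5% | 25.3% | 22.2% | 3.6% | 2.0% to 3.4% |
| 30% / 5% | 21.9% | 24.8% | 25.1% | 3.2% | 3.4% to 3.6% |
| 40% / 10% | 18% | 18% | 17% | 3% | 2% to 3% |
| 10% / 10% | 6.4% | 9.5% | 12.6% | 0.6% | 0.9% to 2.1% |

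Masking of any size therefore needs LECS patients to be a minority. The last row shows that the same pattern arises by chance when the two operations carry equal risk.

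**What would be hidden?** With 2 to 4 LECS patients it is usually one event, because a second can be reached only in patient 10. The exact 95% interval for 1/4 is 0.6% to 80.6%, and for 0/4 it is 0% to 60.2%. Such counts cannot separate a LECS risk above 20% from one below it.

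**Would a count by operation be a better stopping rule?** Not as it stands. At a true 10% risk for both operations, the pooled rule stops with probability 35.4%. The same 20% limit applied within each operation stops with probability 43.5% to 53.6% for f of 2 to 5. A split limit would stop more trials of acceptable procedures on very few patients.

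**Sensitivity to the reading of the rule.** The 20% sentence is not expressly tied to the three-case looks. If it applied after every case, an event in case 4 would stop the trial at 1/4 = 25%, and the stopping probability at 10% / 10% would rise from 35% to 40%. Masking would then be somewhat rarer than tabulated.

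**The case for a change.** The strongest argument for the concern is that the stopping count and its denominator are fixed in the protocol and cannot be put down to an analysis plan that is not at hand. The gastrectomy benchmark matters most for the operation that resects stomach, and in a phase 1 trial with safety as its primary outcome a by-operation listing costs almost nothing.

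Part of this stands. The stopping count is pooled, the arithmetic is right, and the pooled rate alone supports no conclusion about LECS. Showing the results by operation would be good practice.

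None of it shows an error. The pooled count answers the stated objective, and the protocol makes no separate safety claim for LECS. The primary outcome is only defined as a grade threshold, and nothing in the protocol rules out reporting it by operation. Nor is the pooled rate the only safety information. Leakage or abscess, the outcome most likely to reveal harm from opening the gastric wall, is a named secondary outcome. Complications are monitored case by case. That sentence most naturally refers to each operation performed and sets no limit by type, but it means each event is reviewed with its operation known. An event in the first three cases, or a procedure-attributed death, ends the trial whichever operation was used.

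**Conclusion.** The concern does not hold. Pooling fits an objective framed as one strategy with or without LECS. The 20% ceiling on a completed trial comes from the look schedule. It also presumes that complications in cases 1 to 9 are known before case 10, and would apply equally to a single operation. Masking ranges from about 2% to 25% in the scenarios with unequal risks, entirely on assumed risks and an assumed LECS share. It falls to about 2% to 4% once half or more of the patients have LECS, and where it is larger it usually rests on one patient. Separate counts in a ten-patient, single-centre series would be descriptive. They belong in tables that a protocol commonly leaves to the statistical analysis plan, and they would change no stopping decision and no result that the protocol states.

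### The death stopping rule turns on an undefined attribution, and the all-cause mortality outcomes trigger no stop or pause, so enrolment can continue after an early death judged unrelated

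*Protocol*

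**What the plan says.** The Protocol's section Assessment of safety sets two stopping rules. The first concerns deaths: "If any death is observed directly attributed to the procedure the study will be prematurely discontinued". The second stops the study when Clavien-Dindo grade III or higher complications exceed 20% of cases. That section also says: "Complications will be continuously monitored for each procedure according to the clinic's routines", and "An interim analysis will be performed for each 3 cases completed".

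On recording deaths, Follow-up says: "For patients who die before completing follow-up, the date of death will be documented". Cause of death and relation to the procedure are not named as data items anywhere in the protocol.

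Secondary outcome measures lists "30-day mortality" and "In-hospital mortality", neither with an attribution condition. The Study flowchart schedules review of medical charts at the 30-day visit and at 12 months. Study design describes "A single-center, phase-1, prospective non-randomized trial", and Sample size plans 10 patients.

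**The concern.** Safety is the primary outcome, and the rule for the gravest event depends on a causal judgment that the protocol leaves open. It does not say what makes an attribution direct, who decides, how long after surgery the rule applies, or what happens while the cause is uncertain. A postoperative death put down to a cardiac event, a pulmonary embolism or comorbidity could be classed as not directly attributed and leave the rule untouched.

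The protocol already measures two endpoints that need no such judgment, 30-day and in-hospital mortality, but no action follows from either. In an uncontrolled study of 10 patients there is no comparison group to show whether an early death was to be expected. At stake is whether further patients can be enrolled before anyone is required to establish why an earlier patient died.

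**Working it through.** The plan gives no figure to reproduce here. The check is whether the 20% rule catches a single early death that the death rule lets pass.

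**Inputs**
- Threshold: strictly more than 20% of cases (Assessment of safety).
- Looks: after every 3 completed cases, so at 3, 6 and 9 (Assessment of safety).
- Planned total: 10 patients (Sample size).
- Scenario: one death, judged not directly due to the procedure, is the only severe event.
- Assumption: death counts as grade III or higher. The primary outcome sets no upper grade, which supports this, but the protocol does not spell it out, and its secondary outcome for any complication lists grades II to IV only.

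**Formula.** One event among n cumulative cases exceeds the threshold when 1/n > 0.20, that is, when n < 5.

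| n | 1/n | Above 20%? |
|---|---|---|
| 3 | 33.3% | yes |
| 4 | 25.0% | yes |
| 5 | 20.0% | no (equal) |
| 6 | 16.7% | no |
| 9 | 11.1% | no |
| 10 | 10.0% | no |

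The protocol does not say whether the percentage is cumulative or per block, or whether it is checked only at the looks. The result depends on the reading:

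1. **Cumulative, checked at the looks.** One event is enough at 3. Two are needed at 6 (2/6 = 33.3%) and at 9 (2/9 = 22.2%). A lone death in case 4 or later triggers nothing: cases 4 to 10, or 7 of 10 patients.
2. **Cumulative, checked after every case.** One event is enough up to case 4. A lone death in cases 5 to 10, or 6 of 10 patients, triggers nothing.
3. **Per block of three.** One event is 1/3 = 33.3% in any block, so a counted death in cases 1 to 9 exceeds the threshold. Only case 10 falls outside a full block.
4. **Death not counted as a complication.** It adds 0 to the count, and neither rule triggers at any look, whichever case it is.

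**Timing.** The looks do not hold enrolment in between. If the patient in case 4 dies before the next operation, cases 5 and 6 can still be done before the look at 6. The same holds for case 7 and cases 8 and 9. After case 10 there is no further look.

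**The case against.** The strongest reply is that the two rules form a coherent, overlapping design: one for deaths caused by the procedure, one for severe complications generally. No statement in the protocol contradicts another. The scenario needs an early death that is also judged unrelated and is the only severe event, in patients from whom those inoperable because of severe comorbidity have been excluded. The protocol gives no figure from which its likelihood could be worked out. Who attributes deaths may also be settled in a document that is not shown. All this is fair, and it makes the point an improvement rather than an error.

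A reader might infer four stronger claims, which the protocol does not support:

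- **That the date is the only thing documented about a death.** The Follow-up sentence names only the date, but it does not exclude other data. Mortality outcomes, chart review and complication monitoring could supply the cause. What stands is that nothing requires cause or relatedness to be recorded.
- **That a death would go unreviewed.** Complications are monitored continuously, and an interim analysis follows every third case. What stands is that no death-specific review is required and enrolment is not held meanwhile.
- **That the operating team judges its own deaths and so leans towards continuing.** The single-center setting and reliance on clinic routines make this plausible, but the text names no assessor.
- **That exactly 6 of the 10 patients are unprotected.** That figure holds only for a cumulative count checked after every case. The working above shows 7 at the stated looks and 1 per block of three.

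None of this links the all-cause mortality outcomes to a stop or a pause.

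**Conclusion.** The point holds in a limited form. The death rule depends on an attribution for which the protocol gives no criterion, assessor or time window, and an early death judged unrelated lets enrolment continue under the plan as written. The 20% rule covers part of this gap. How much depends on two things the protocol leaves open: whether such a death counts as a grade III or higher event, and whether the percentage is cumulative. On a cumulative count at the stated looks, the rule catches a lone counted death only in the first three cases; per block of three it catches one anywhere up to case 9; an uncounted death is never caught. The change is worth making because it is cheap and its trigger is objective and already measured. It does not show that the existing discontinuation rule is wrong.

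**What to change.** Make two additions and leave the present discontinuation rule unchanged.

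- In Assessment of safety, add: any death within 30 days or during the hospital stay, whatever its presumed cause, holds enrolment until its cause and its relation to the procedure have been reviewed and documented.
- In Follow-up, have the cause of death recorded as well as the date.

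The cost is two sentences of protocol text, with no new visits or staff. The downside is that an early death that proves unrelated would briefly pause recruitment.

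### Does the differing Clavien-Dindo cut-off in the Background, or the advanced-cancer source, undermine the 20% stopping benchmark?

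*Protocol*

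**What the plan says.** The Background reports: "Gastrectomy with lymphadenectomy carries a risk of severe complications (Clavien-Dindo grade >IIIa) ranging from 8.9% to 22% (4-6"). Read literally, that cut-off leaves out grade IIIa.

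The primary outcome is "Safety, defined as Clavien-Dindo complication grade >/= III", which includes IIIa. The Assessment of safety section uses the same grade for its rate-based rule: "the study will also be discontinued if severe complications (Clavien-Dindo complication grade" III or worse) exceed 20% "of cases, which is the expected rate for gastrectomy (6"). A separate rule covers procedure-related death. An interim analysis follows every 3 completed cases. The planned size is 10 patients, and no power calculation is made because the study is a pilot.

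On population, the Study population section states: "Patients with EGC previously treated with ESD at our institution will be eligible for inclusion in the study if the resection is non-curative". In the reference list, the title of reference 6 is "Improved survival after laparoscopic compared to open gastrectomy for advanced gastric cancer: a Swedish population-based cohort study", and that of reference 4 includes "following robotic and laparoscopic gastrectomy for advanced gastric cancer: a retrospective and propensity score-matched study". The title of reference 5 is not limited to advanced disease.

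**The concern.** Reference 6 is cited in two places. In the Background it is one of three sources for a rate labelled as worse than IIIa. In the stopping rule it is the only source for 20% at grade III or worse. If the Background label is right for reference 6, the 20% leaves out IIIa events that the trial counts, and the benchmark is too low for them. If the label is a slip for IIIa or worse, which is the same as III or worse, the grade conflict disappears. The protocol does not say which.

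The population raises a second doubt. A rate from gastrectomy for advanced cancer is used, without comment, as the benchmark for patients with early cancer after non-curative ESD.

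The 20% is the only rate-based stopping threshold, and readers are likely to judge the observed complication rate against it. A mismatch could stop the trial too readily or too late, or make the comparison with gastrectomy unlike for like.

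**Working it through.** **What can be reproduced.** The 20% is cited, not calculated. The protocol gives no event counts by grade from reference 6, so there is nothing to re-derive. It lies inside the Background range of 8.9% to 22%.

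**The cut-offs side by side**

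| Place | Cut-off | Role |
|---|---|---|
| Background | worse than IIIa | introductory range, three sources cited together |
| Primary outcome measures | III or worse | endpoint |
| Assessment of safety | III or worse | stopping event, paired with 20% in the same sentence |

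The two places that govern the trial agree. The joint citation in the Background does not say which figure, or which grade, comes from reference 6.

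**How sensitive the rule is to the benchmark.** Inputs are the threshold (more than 20%), the interval of 3 cases and the planned 10 patients, all from the protocol. I take the rule as applied at cases 3, 6 and 9, stopping if events/n exceeds the threshold.

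Observed proportions near the threshold are 1/3 = 33.3%; 1/6 = 16.7% and 2/6 = 33.3%; 1/9 = 11.1%, 2/9 = 22.2% and 3/9 = 33.3%. The minimum stopping counts follow:

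| Benchmark | At 3 | At 6 | At 9 |
|---|---|---|---|
| 8.9% | 1 | 1 | 1 |
| 16.7% to just under 22.2% (includes 20% and 22%) | 1 | 2 | 2 |
| 22.2% to just under 33.3% | 1 | 2 | 3 |

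Stopping probability at a true rate of 20%, with the 20% threshold:

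- Case 3: 1 − 0.8³ = 0.488. The trial continues with no event: 0.512.
- Case 6: P(2 or more events in 3) = 3 × 0.2² × 0.8 + 0.2³ = 0.104, and 0.512 × 0.104 = 0.053. It continues with no event: 0.512 × 0.512 = 0.262. It continues with one event: 0.512 × 0.384 = 0.197.
- Case 9: 0.262 × 0.104 + 0.197 × 0.488 = 0.123.
- Total: 0.488 + 0.053 + 0.123 = 0.664.

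With a benchmark from 22.2% to just under 33.3%, only the last step changes: 0.262 × 0.008 + 0.197 × 0.104 = 0.023, total 0.564. With 8.9%, one event stops at any look: 1 − 0.8⁹ = 0.866. At a true rate of 30% the three totals are 0.856 (20% threshold), 0.767 and 0.960.

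**How large a grade mismatch would have to be.** Suppose 20% is a IIIb-or-worse rate and IIIa makes up a share s of all events of grade III or worse. The matching rate is 0.20/(1 − s).

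- It reaches 2/9 when 1 − s = 0.90, so s = 10%.
- It reaches 1/3 when 1 − s = 0.60, so s = 40%.

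Below 10% no count changes. From 10% to just under 40% only the count at case 9 changes. The documents do not give s.

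**The case for a change.** The strongest case for a change is that a slip cannot be proven from the text. The same term, severe complications, carries two definitions, and either explanation calls for a look at reference 6. A statistical analysis plan cannot repair wording fixed in the protocol. A IIIa share of only 10% would already move the count at case 9. The population point remains whatever the grade label means: if the right benchmark for early cancer were below 16.7%, the count at case 6 would change too, and at 8.9% the chance of stopping at a true rate of 20% would be 86.6% rather than 66.4%.

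Part of this stands. The Background label does not match the rest of the protocol, and the source population of the 20% is not mentioned where the figure is used. Whoever reports the trial should name that population.

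The rest does not carry. The protocol never adopts 8.9%, and nothing in it says that early-cancer gastrectomy has a lower or higher rate. A grade mismatch, if real, would make the rule stop sooner, which is the cautious direction for participants. The benchmark is for gastrectomy, the operation this procedure is meant to replace, and it comes from a Swedish population-based cohort for a trial run in Stockholm. That is a visible, if unargued, reason for choosing it. The protocol plans no formal comparison of the primary outcome with 20%.

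**Conclusion.** No change to the plan follows. The grade discrepancy is most simply read as a clerical slip in a Background sentence. It touches neither the endpoint nor the stopping event, which agree. Using an advanced-cancer gastrectomy cohort as a benchmark in a 10-patient pilot is a fair choice whose reasoning is left unstated.

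The possible effect of a grade mismatch is small. No stopping count changes for any benchmark from 16.7% to just under 22.2%, which includes the top of the protocol's own range. Up to just under 33.3% the only change is 3 events instead of 2 at case 9, when one planned patient remains. At a true rate of 20% that is 66.4% against 56.4%. Of the 66.4 points, 54.1 (48.8 + 5.3) arise at the first two looks and would not move.

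This rests on looks at cases 3, 6 and 9 and on the proportion being taken over cases completed so far. The content of reference 6 cannot be checked here, so the conclusion is that 20% has not been shown to be wrong, not that it has been confirmed. Aligning the label and naming the source population would tidy the text but would leave the endpoint and threshold as they are.
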